Pulmonary embolism (PE) is an insidious disease, frequently not recognized or mistaken for other pathologies, and is accompanied by a high mortality rate if not properly identified and treated (1). The onset modalities that often lead to erroneous diagnostic conclusions include angina-type chest pain, right or congestive heart failure, the exacerbation of chronic obstructive pulmonary disease, pneumonic pulmonary thickening, pleuritic pleural effusion and syncope (2). Recently it has been shown that the application of an adequate diagnostic algorithm can allow the recognition of PE in over 17% of patients hospitalized for a syncopal episode (3). In the PIOPED II study, 16% of patients with documented PE had come to the observation for exertional dyspnea, that is, a shortness of breath for physical activities that usually do not determine it (4). The most common cause is congestive heart failure. Other conditions that can cause it are chronic obstructive pulmonary disease, lung disease (e.g. pneumonia), aortic stenosis, severe anemia, hyperthyroidism, lung cancer, liver and kidney disease and psychopathological disorders. Although PE has been identified among the conditions that can cause exertional dyspnea (4), it is rarely suspected and its prevalence in subjects who reach the Emergency Departments for this condition is unknown.

The international guidelines for the diagnostic approach to patients with suspected EP recommend the use of a clinical probability score in combination with the result of a laboratory test, the D-Dimer (2). The most commonly used stratification model is the one described by Wells and associates, which scores a number of partly anamnestic and partly clinical parameters, and allows to identify as having a high pre-test clinical probability those subjects who score at least 4 (5). Based on the results of several clinical studies, patients with both a low clinical probability and negative D-Dimer can be regarded as not having PE (2). Accordingly, these patients do not require further diagnostic tests. In order to reduce the risk of false positivity D-Dimer tests (test of high sensitivity to thromboembolism, but of poor specificity), an algorithm that takes into account the patient's age has been successfully tested in subsequent studies of wide international impact. More specifically, it has been shown that with the adoption of sensitive D-dimer tests (cutoff 500 ng/ml) it is safe to withhold pulmonary CT angiography from patients older than 50 years whose laboratory test does not exceed a value that is achieved by multiplying their age by 10 (6).

General Aims and Study Objectives

This observational, cross-sectional, multicenter Italian study aims at investigating the prevalence of PE in a consecutive series of patients who refer to the Emergency Departments (either spontaneously or sent by their attending physicians) for the recent (less than one months) development of exertional dyspnea.

Objectives

To assess the prevalence of PE (and its 95% CI) in the overall population as well as in relevant subgroups (patients who will be imaged, patients without potential explanations for dyspnea).

Investigational Plan

Study design

The PEDIS study is an observational study, national multicenter and no Profit.

Setting

Emergency departments

Timeline

Data planned for the study beginning (first patient enrollment): 1 July 2018

Data planned for the last patient enrollment: 1 September 2019 or the achievement of the target of 600 patients.

Study population

All consecutive patients who refer to the Emergency Departments of the participating centers will be eligible for the study provided they are older than 18 and younger than 75 years, and have developed one or more episodes of exertional dyspnea since less than one month.

Inclusion Criteria

Subjects meeting the following criteria

- Age older than 18 and younger than 75
- Recent (less than one month) development of exertional dyspnea

Exclusion Criteria

Subjects meeting the following criteria:

- Anticoagulation required for other indications
- Contraindication to CT angiography (allergy to the contrast dye, severe renal failure [creatinine clearance < 30 ml/min])
- Involvement in simultaneous clinical trials
- Unable to provide their written informed consent

Study Procedures

Enrolment Procedures

All eligible patients will be interviewed and examined by trained study physicians. The presence of already known potential explanations for the dyspnea (see before) will be assessed. In addition, symptoms of the lower extremities will be elicited, as well as the presence of risk factors for venous thromboembolism (VTE), including recent surgery, trauma or infectious disease, ongoing hormonal treatment, prolonged immobilization, active cancer and history of VTE. The severity of dyspnea will be classified according to the modified scale of the Medical Research Council.

The presence or absence of pulmonary embolism will be assessed with the use of a validated algorithm based on pre-test clinical probability and D-dimer result. The D-dimer level will be assessed with the quantitative assay routinely used in each participating center, and the cut-off will be adjusted to patients age in a standardized fashion. The pre-test clinical probability will be assessed by the simplified Wells score that classifies it as being “likely” or “unlikely”. In patients in whom the pre-test clinical probability is low (“unlikely”) and the D-dimer result is negative, no further testing will

be done, and PE will be considered excluded. In patients with high clinical probability, positive D-dimer result, or both, computed tomography (CT) pulmonary angiography will be performed. Criterion for the presence of PE will be an intraluminal filling defect on CT angiography. In patients with PE, the thrombotic burden will be assessed by a central adjudication committee through the identification of the most proximal location of the embolus on CT angiography.

Definition of the conclusion of the study

Stoplines:

- after enrolling 300 patients, if the lower limit of the 95% CI of the prevalence of PE is $\geq 20\%$;
- otherwise:
- after enrolling 600 patients

Outcome of the study

Primary endpoint

- Prevalence of PE in the overall population

Secondary endpoints:

Prevalence of PE in the following subgroups:

- patients with high pre-test clinical probability and/or positive D-dimer
- patients without potential explanations for the dyspnea
- each of the 5 severity groups of the modified scale of the Medical Research Council

Statistical consideration

Bias

To avoid patient's selection bias, the investigators are asked to consecutively include the observed patients or, if it is not possible, to declare the criterion adopted for enrolment (e.g. one day a week, one week a month, etc.).

Sample size

Based on pilot data, we assume a prevalence of PE in patients with dyspnea on exertion between 10 and 15%. In order to obtain a two-sided 95% confidence interval (CI) of 2.5% for the prevalence of PE, we estimate that a sample size of 550 patients is required. All centers will be asked to contribute patients until the achievement of the overall sample size.

Statistical analysis plan

The prevalence of PE and the associated 95% CI will be calculated for the entire group of patients and for relevant subgroups. For comparison of baseline characteristics between patients with and without PE, the chi-square test will be used for categorical parameters, while the Student's t-test will be used for continuous parameters. Odds ratios and their 95% CIs will be calculated using logistic regression. The 95% CIs and P values will be calculated according to the normal approximation of the binomial distribution. No adjustments will be made for multiple testing.

An interim analysis will be performed after the inclusion of 300 patients. If the lower limit of the 95% CI around the prevalence of PE is $\geq 20\%$, the study will be interrupted.

Study administration

Data collection and management

Patient's personal data will be collected (in anonymous form), date of birth, gender, weight, height, liver and hepatic enzymes, past clinical history, thrombotic/haemorrhagic risk factors, lifestyle habits, type of treatment

The monitor of the study will check data quality and completeness by remote monitoring.

Data will be anonymously entered by the investigator in the eCRF, by assigning a patient identification code.

The adopted database is REDCap stored in the server owned by Fondazione Arianna Anticoagulazione, which is responsible for maintaining, and backing up the database..

Each access to the eCRF will be managed by personal user name and a password.

The security system requires that the password be changed at the first access; it requires a length of at least 8 characters and provides for a periodic 3-month expiry.

It is obviously possible to disable the login, if it is deemed necessary by the system administrator.

Investigators can have full access only to their patient's data.

Every night the data backup is automatically performed.

Ethics

The study will be conducted in accordance with the ethical principles that have their origin in the Declaration of Helsinki and in compliance with the protocol and ICH-GCP.

This is an observational study and all drug prescriptions and clinical investigations are independent from the study.

The protocol and any amendments and the informed consent form (or information/non-opposition letter, as allowed by local regulations) will have to obtain Institutional Review Board or Ethics committee (IRB/EC) approval prior to initiation of the study.

Informed Consent Form

Participation in this study is entirely voluntary. Informed consent will be obtained in accordance with the Declaration of Helsinki, ICH GCP and local regulations. A properly executed, written, informed consent will be obtained from each subject prior to entering the subject into the trial. Information should be given in both oral and written form and subjects (or their legal representatives) must be given ample opportunity to inquire about details of the study. If appropriate and required by the local IRB/IEC, assent from the subject will also be obtained. If a subject is unable to sign the informed consent form (ICF) a legal representative may sign for the subject. A copy of the signed consent form will be given to the subject or legal representative of the subject and the original will be maintained with the subject's records. Once a patient has been enrolled in the study, he/she may withdraw his/her consent to participate in the study at any time without prejudice. Patients will not be entered in the database if the informed consent has not been obtained.

Procedures implemented to guarantee data confidentiality

The investigators collected patient's personal data in anonymous form by assigning a patient identification code.

The adopted database is RedCap. Data anonymously entered in the eCRF will be recorded and stored in the server owned by Fondazione Arianna Anticoagulazione. Each access to the eCRF will be managed by personal user name and a password.

The security system requires that the password be changed at the first access; it requires a length of at least 8 characters and provides for a periodic 3-month expiry.

It is obviously possible to disable the login, if it is deemed necessary by the system administrator. Investigators can have full access only to their patient's data. Every night the data backup is automatically performed.

Administrative Issues

Support of the study

Participation in the PEDIS study is entirely voluntary and no form of remuneration or refund is given to the investigators.

The PEDIS study is supported by own funds of the Promoter, for the preparation, working and maintenance of all the necessary activities, i.e. informatic and monitoring activities, statistical analysis of results, production of reports and publication of scientific papers.

Publication

Role of Promoter and Investigators

The Promoter and the investigators may suggest specific analysis, regarding all or some data of the central database. The authorship of the article must provide who proposed the analysis, who performed the data analysis, who took part in writing the article.

Data handling and record keeping

All data and results and all intellectual property rights to the data and results derived from the study will be the property of the Promoter Fondazione Arianna Anticoagulazione according to D.M. 17 Dicembre 2004. This study is a No Profit Study (D.M. 17 Dicembre 2004, Art. 1, comma 2, lettera c).

Final report and publication

Within 12 months from the completion of the trial and in accordance with ICH-GCP, the promoter provides the IRB/IEC with a summary of the trial's outcome, and the regulatory authority(ies) with any reports required. All data and results and all intellectual property rights to the data and results derived from the study will be the property of Fondazione Arianna Anticoagulazione, who may utilize the data in various ways, such as for submission to government regulatory authorities or disclosure to other investigators. All publication or communication (oral or written) will respect the international requirements: "Uniforms requirements for Manuscripts Submitted to Biomedical Journals".

References

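### Neither 550 nor 600 patients gives a 2.5-point 95% CI half-width across the assumed 10–15% prevalence range; the claim holds only near 10%

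*Combined protocol and SAP*

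**What the plan says.** Under Statistical consideration, Sample size, the plan cites pilot data: "we assume a prevalence of PE in patients with dyspnea on exertion between 10 and 15" per cent. It names no single design value within that range. It then sets the precision target and the number together: "two-sided 95% confidence interval (CI) of 2.5% for the prevalence of PE, we estimate that a sample size of 550 patients is required". It does not say whether 2.5% is a half-width or the full width of the interval. The section closes by asking centres to keep recruiting until the overall size is reached, and the only size given there is 550.

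The Statistical analysis plan fixes the interval method: "The 95% CIs and P values will be calculated according to the normal approximation of the binomial distribution".

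Two other places use a different number. Under Stoplines, unless the interim rule at 300 patients is met, the study ends "after enrolling 600 patients". Under Timeline, enrolment closes at "1 September 2019 or the achievement of the target of 600 patients". No reason is given for the step from 550 to 600.

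**The concern.** For a proportion below 50%, the absolute width of the confidence interval grows as the proportion rises. If the prevalence may lie anywhere from 10% to 15%, the hardest case is 15%, and a sample size meant to deliver a given precision over that range has to be set there. The figure of 550 looks as though it was set at 10%, the most favourable end, without saying so.

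The primary endpoint is the prevalence of PE in the overall population. There is no primary hypothesis and no power statement, so the width of this interval is the whole quantitative case for the number of patients. If the width is not delivered over most of the plan's own assumption, the stated justification does not support the design, and a reader cannot see that a best-case input was used.

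**Working it through.** **Inputs**

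- Prevalence p: 10% to 15% (Sample size).
- Confidence level: two-sided 95%, so z = 1.95996 and z² = 3.8415 (Sample size).
- Precision d: 2.5 points, taken as a half-width, 0.025 (Sample size; this reading is tested below).
- Interval method: normal approximation (Statistical analysis plan).
- Patients n: 550 (Sample size) and 600 (Stoplines, Timeline).

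**Step 1. Reproduce the plan's figure.** The formula is n = z² p(1−p) / d², where z²/d² = 3.8415 / 0.000625 = 6146.3.

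- p = 0.10: 6146.3 × 0.0900 = 553.2, rounded up to 554
- p = 0.125: 6146.3 × 0.109375 = 672.3, rounded up to 673
- p = 0.15: 6146.3 × 0.1275 = 783.7, rounded up to 784

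The stated 550 is reproduced, to rounding, at 10% only.

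**Step 2. Half-width actually delivered.** The formula is z √(p(1−p)/n), in percentage points.

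| Prevalence | n = 550 | n = 600 |
|---|---|---|
| 10% | 2.51 | 2.40 |
| 12.5% | 2.76 | 2.65 |
| 15% | 2.98 | 2.86 |

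**Step 3. Largest prevalence at which 2.5 points holds.** Solve p(1−p) = n d²/z².

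- n = 550: p(1−p) = 550 / 6146.3 = 0.08948, so p = 9.9%
- n = 600: p(1−p) = 600 / 6146.3 = 0.09762, so p = 11.0%

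With 550 the limit falls just below the assumed range. With 600 it covers 10% to about 11%, which leaves (15 − 11)/(15 − 10) = 4/5 of the range uncovered.

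**Step 4. Does another reading rescue 550?** Required n at 10% and at 15%:

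| Reading | 10% | 15% |
|---|---|---|
| Wilson interval, half-width 2.5 | 557 | 784 |
| Clopper–Pearson, half-width 2.5 | 593 | 822 |
| Normal approximation with continuity correction | 593 | 824 |
| 2.5% as full width (d = 0.0125) | 2,213 | 3,135 |

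None covers the range with 550 or 600. Using z = 1.645 gives 552 at 15%, but that is a two-sided 90% interval and contradicts the stated two-sided 95%. The half-width reading is therefore the one most favourable to the plan.

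**The case against.** The strongest reply is that nothing was miscalculated. The figure of 550 follows from the usual formula at 10%, which lies inside the stated range, and the text does not expressly promise 2.5 points at every prevalence up to 15%. This is correct as far as it goes: the fault is an undisclosed choice of the easiest value, not a slip in the formula. But a sentence that assumes 10–15% and then says 550 is what 2.5% requires will be read as covering that range, and it does not.

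A second reply is that the consequence is small. At 15% with 600 patients the expected interval is 15 ± 2.86, or about 12.1% to 17.9%, instead of 12.5% to 17.5%. No test or decision is tied to 2.5 points, and the achieved interval will be reported in any case. This stands. It limits the harm to the width of the primary estimate and leaves its validity untouched, but it does not make the stated figure right.

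A third reply is that 600 may be a deliberate margin over a minimum of 550 (600/550 = 1.09, about 9% more). That is possible, so the two numbers are better called an unexplained difference than a proven contradiction. Still, the plan mentions no allowance for non-evaluable patients, and the Sample size section on its own tells centres to stop at a different number from Stoplines and Timeline. Whatever the reason for 600, it does not restore 2.5 points above about 11%.

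**Conclusion.** The concern holds. Under the plan's own interval method and the reading of 2.5% most favourable to it, the stated precision is met only up to a prevalence of 9.9% with 550 patients and 11.0% with 600. At the top of the assumed range the half-width is 2.98 or 2.86 points, a shortfall of 0.48 or 0.36 points. Holding 2.5 points at 15% would take 784 patients, which is 184 more than the 600 target.

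This rests on taking the assumed 10–15% at face value and on 2.5% meaning a half-width. If it meant full width, the shortfall would be far larger. The statement should be corrected because it is the sole justification for the sample size, although the practical effect on the result is modest.

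**What to change.** Replace the precision sentence under Sample size with one that states what the design delivers, for example:

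> With 600 patients, the half-width of the two-sided 95% CI (normal approximation) will be 2.4 percentage points at a prevalence of 10%, 2.65 at 12.5% and 2.9 at 15%.

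Add a line saying that about 2.9 points is considered adequate for the study's purpose. Use 600 as the single sample size under Sample size, Stoplines and Timeline; if 550 is kept as a minimum, say so and explain the margin. Because Timeline also allows enrolment to close on a calendar date, note that precision will be lower if fewer than 600 are enrolled (with 550: 2.5, 2.8 and 3.0 points at the same three prevalences).

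The cost is wording only: no added patients and no change to the analysis. The stated precision becomes slightly less favourable at the upper end, about 2.9 points instead of 2.5.

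### Student's t-test is planned for groups of about 60–90 and 510–540 patients, where it is not robust if the two spreads differ materially; naming Welch's test, on the log scale for skewed values, is a minor and cheap improvement

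*Combined protocol and SAP*

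**What the plan says.** The Statistical analysis plan introduces the analysis with "For comparison of baseline characteristics between patients with and without PE". It assigns the chi-square test to categorical variables and states that Student's "t-test will be used for continuous parameters". It names no unequal-variance version, transformation or rank test.

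The group sizes follow from two other places. Under Sample size: "we assume a prevalence of PE in patients with dyspnea on exertion between 10 and 15" per cent. Under Definition of the conclusion of the study, recruitment ends "after enrolling 600 patients" unless the interim rule at 300 is met.

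Data collection and management lists "date of birth, gender, weight, height, liver and hepatic enzymes" among the data to be recorded, so both roughly symmetric and typically right-skewed variables are available for comparison.

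**The concern.** Student's test estimates one common variance. When one group is six to nine times larger than the other, that estimate is almost entirely the variance of the larger group. The mean of the smaller group, however, contributes most of the uncertainty in the difference. If patients with PE are the more variable group, the standard error is too small and the test rejects too often. If they are less variable, the standard error is too large and real differences are missed.

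The groups are formed by the diagnostic outcome and not by randomisation, so nothing in the design makes the variances equal. At stake is the meaning of the p-values in the baseline comparison. The plan also makes no adjustment for multiple testing, and a reader could not tell whether a given p-value is too small or too large.

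**Working it through.** **The plan's own figure.** The documents give no figure for the t-test. The one sample-size figure is "we estimate that a sample size of 550 patients is required", for a "two-sided 95% confidence interval (CI) of 2.5% for the prevalence of PE". Reading 2.5% as the half-width, n = 1.96² × 0.10 × 0.90 / 0.025² ≈ 553, so 550 reproduces at the 10% end of the assumed range.

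**Inputs.**
- Total 600 (Definition of the conclusion of the study); prevalence 10–15% (Sample size).
- Group sizes: 600 × 0.10 = 60 versus 540; 600 × 0.15 = 90 versus 510; midpoint 600 × 0.125 = 75 versus 525.
- Assumed, because the documents do not state them: SD ratio r (PE to no PE) from 0.5 to 2, and a two-sided 5% level.

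**Formula.** With n1 patients with PE, n2 without, and the no-PE SD set to 1:

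- pooled SE = √{[((n1−1)r² + (n2−1)) / (n1+n2−2)] × (1/n1 + 1/n2)}
- true SE = √(r²/n1 + 1/n2)
- true error ≈ 2 × P(Z > 1.964 × pooled SE / true SE)

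**Example, 75 versus 525, r = 1.5.** Pooled variance = (74 × 2.25 + 524)/598 = 1.155. Pooled SE = √(1.155 × 0.01524) = 0.1326. True SE = √(2.25/75 + 1/525) = 0.1786. The ratio is 0.743, and 2 × P(Z > 1.459) = 14.5%.

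**Range of group sizes.** SE ratios are from the formula; error rates are from simulation with 200,000 normal replicates per setting.

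| SD ratio | SE ratio, 60/540 | Student error, 60/540 | SE ratio, 90/510 | Student error, 90/510 |
|---|---|---|---|---|
| 0.5 | 1.688 | 0.1% | 1.565 | 0.2% |
| 0.67 | 1.370 | 0.7% | 1.314 | 1.0% |
| 0.8 | 1.194 | 1.9% | 1.168 | 2.2% |
| 0.9 | 1.088 | 3.4% | 1.077 | 3.6% |
| 1.0 | 1.000 | 5.0% | 1.000 | 5.0% |
| 1.1 | 0.927 | 6.9% | 0.935 | 6.7% |
| 1.25 | 0.837 | 10.1% | 0.856 | 9.3% |
| 1.5 | 0.727 | 15.4% | 0.758 | 13.8% |
| 2.0 | 0.592 | 24.4% | 0.638 | 21.1% |

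Welch's test stayed at 4.9–5.1% in all these settings. With 550 patients (55/495 or 82/468) the results are practically the same. With equal groups (300/300) Student's test stays at about 5% at every ratio, so the distortion comes from the imbalance.

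**Power when the PE group is less variable (75 versus 525, r = 0.67, difference 0.25 of the no-PE SD).** True SE = √(0.67²/75 + 1/525) = 0.0888, so the standardised difference is 0.25/0.0888 = 2.81. The pooled SE is 1.341 times the true SE, so Student's test in effect requires 1.964 × 1.341 = 2.63. Its power is P(Z > 2.63 − 2.81) ≈ 57%. Welch's test requires about 1.98, which gives about 80%.

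**Early stop.** The plan states: "An interim analysis will be performed after the inclusion of 300 patients". Stopping needs a lower limit of at least 20%. With 75 of 300, 0.25 − 1.96 × √(0.25 × 0.75/300) = 20.1%, which passes; 74 of 300 gives 19.8%, which does not. The groups would then be 75 versus 225 or closer to balance. At 75 versus 225 the error is 10.8% at r = 1.5 and 15.1% at r = 2.

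**Skewed data.** With identical lognormal distributions in both groups (log-SDs assumed, 75 versus 525), Student's test holds at about 5%. Welch's test on the raw scale rejects in 7.1% at log-SD 1.0 and 10.1% at log-SD 1.5.

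**The case against.** The case for leaving the plan alone has several sound parts.

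- **Small differences in spread do little harm.** A reader might infer that the test fails whenever the SDs differ. It does not: a 10% difference moves the error only to about 3.5% or 7%. The effect becomes material at ratios of about 1.25 and above, or 0.8 and below. With no SDs in the documents, the actual size is unknown.
- **Neither a test level nor an interval for a mean difference is stated.** The confidence intervals named are for prevalence and odds ratios. A claim that planned 95% intervals for mean differences are wrong has no support; it would apply only if such intervals were reported.
- **Skewness is a different matter from unequal variance.** If both groups share the same skewed distribution, Student's test holds its level and raw-scale Welch does not. This stands, and it rules out prescribing Welch's test on the raw scale for every variable.
- **D-dimer is a poor example.** Under Enrolment Procedures it helps decide who is imaged and who is declared free of PE, so the groups differ on it by construction and a false-positive rate means little. It is also measured with each centre's own assay.
- **The comparisons are supporting.** No objective concerns predictors of PE, and the planned logistic regression may also cover continuous variables, so the t-tests need not be the only analysis of them.

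What remains is that the plan names a test that is fragile at the plan's own group sizes, while a more robust one costs almost nothing.

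**Conclusion.** The point holds as a minor one. If the SD ratio is 1.5 to 2, a nominal 5% test has a true error of about 14–24%. If it is 0.67, the error is about 1% and power at the midpoint group sizes falls from about 80% to 57%. An interim stop at 300 would lessen the distortion.

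This rests on four assumptions: the pooled form (inferred from the test's name), a two-sided 5% level, roughly normal data, and SD ratios that the documents neither give nor exclude.

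A reader might go further and infer that the study's conclusions are at risk. The documents do not support that. The primary endpoint and all secondary endpoints are PE prevalences, the stopping rule uses the prevalence interval, and none of them uses the t-test.

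**What to change.** In the Statistical analysis plan, replace Student's t-test with Welch's unequal-variance t-test for roughly symmetric continuous parameters. Add that clearly right-skewed laboratory values, such as enzymes, will be compared with Welch's test on the log scale. The two parts belong together, because Welch's test on the raw scale is too liberal for strongly skewed data at this imbalance.

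The cost is a sentence or two and no new data. When the SDs are equal, about half a percentage point of power is lost (80.6% to 80.1% for a 0.35 SD difference with 75 versus 525). Log-scale results are read as ratios of geometric means, which the table should state.

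### The normal-approximation interval, read as Wald, sets the upper limits for PE prevalence by mMRC group too low about twice as often as it should, and the plan names no interval for sparse groups

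*Combined protocol and SAP*

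**What the plan says.** The Statistical analysis plan section promises intervals overall and by subgroup: "The prevalence of PE and the associated 95% CI will be calculated for the entire group of patients and for relevant subgroups". It then fixes one method for all of them: "The 95% CIs and P values will be calculated according to the normal approximation of the binomial distribution". The variant (Wald, continuity-corrected or score) is not named.

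The secondary endpoints include PE prevalence in "each of the 5 severity groups of the modified scale of the Medical Research Council". The Objectives section uses the same phrase about relevant subgroups but illustrates it with two others: "in relevant subgroups (patients who will be imaged, patients without potential explanations for dyspnea". That the mMRC groups also receive intervals by this method is therefore the natural reading, not an explicit statement.

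The planning prevalence is in the Sample size section: "Based on pilot data, we assume a prevalence of PE in patients with dyspnea on exertion between 10 and 15" per cent. Unless the interim rule stops the study at 300 patients, it concludes "after enrolling 600 patients". The documents give no expected mMRC group sizes and no alternative interval for groups with few or no PEs.

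**The concern.** The Wald interval is centred on the observed proportion and takes its width from that same proportion. When a group happens to show few PEs, the estimate is low and the interval is also narrow, so the upper limit tends to fall short. With no events the width is zero. Five subgroups with prevalence near 10–15% are a setting where this can matter.

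What is at stake is the reading of a stated secondary endpoint. The upper limit tells a reader how common PE could be in a given severity group, and limits that are too low too often understate it.

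**Working it through.** **Inputs.** From the documents: two-sided 95% level (2.5% nominal miss per tail); prevalence 10–15%, stated for the overall population; 600 patients; five mMRC groups. Assumed: the Wald reading; 10–15% prevalence within each group; equal groups of 600/5 = 120, then smaller sizes.

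**The plan's own figure.** For half-width h, n = z²p(1−p)/h². With z = 1.96, p = 0.10 and h = 0.025: 3.8416 × 0.09 / 0.000625 = 553.2, so 554, close to the plan's 550. At p = 0.125 the formula gives 673 and at p = 0.15 it gives 784, so 550 fits only the lower end of the assumed range. This agrees with a Wald half-width but does not settle which variant the analysis will use.

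**Method.** With x PEs among n patients and p̂ = x/n:

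- Wald: p̂ ± 1.96 √(p̂(1−p̂)/n).
- Wilson: [p̂ + z²/(2n) ± z √(p̂(1−p̂)/n + z²/(4n²))] / (1 + z²/n).

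For each true p on an even grid from 0.10 to 0.15, binomial probabilities were summed exactly over all x to give coverage, the chance that the upper limit is below p, and the chance that the lower limit is above p.

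**Equal groups of 120.**

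| Interval | Mean coverage (range) | Upper limit too low, mean (range) | Lower limit too high, mean |
|---|---|---|---|
| Wald | 93.6% (91.5–95.5%) | 5.1% (3.4–7.7%) | 1.3% |
| Wald, continuity-corrected | 95.2% (93.5–96.6%) | 3.9% (2.6–5.8%) | 0.9% |
| Wilson | 95.1% (93.7–96.6%) | 1.9% (1.1–2.7%) | 3.0% |
| Clopper-Pearson | 96.4% (95.3–97.6%) | 1.7% (1.0–2.5%) | 1.9% |

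Wald coverage is not below 95% everywhere: it is 95.4% at exactly 10%, 92.9% at 12.5% and 93.9% at 15%. The upper-tail fault is consistent: 5.1/2.5 is about twice nominal on average, and the rate never drops to 2.5% anywhere in the range.

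**Size of the shift.** For 12/120, the Wald upper limit is 0.10 + 1.96 √(0.09/120) = 0.10 + 0.054 = 15.4%; Wilson gives 16.7%. For 18/120 the limits are 21.4% and 22.5%.

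**Five groups together** (independent, one common prevalence; assumptions). The chance that at least one limit errs is 1 − (1 − miss)⁵, and the nominal value is 1 − 0.975⁵ = 11.9%. For upper limits too low: Wald 23.1%, Wilson 8.9%. For lower limits too high: Wald 6.3%, Wilson 14.3%.

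**Other sizes, Wald, 10–15% prevalence** (all subgroup sizes assumed).

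| n | Mean coverage | Upper limit too low, mean | Smallest value in range |
|---|---|---|---|
| 600 (overall) | 94.7% | 3.4% | 2.9% |
| 90 | 93.2% | 5.6% | 3.5% |
| 60 | 92.4% | 6.6% | 3.9% |
| 40 | 91.4% | 7.7% | 4.3% |
| 30 | 88.9% | 10.3% | 4.8% |
| 20 | 90.7% | 8.6% | 4.3% |

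The decline is not monotone, nor present at every prevalence: at exactly 15%, n = 60 (94.4%) and n = 30 (94.2%) cover better than n = 120 (93.9%). Wilson averages 95.1–96.1% at n = 20 to 120.

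**Group prevalence outside 10–15%** (assumed), n = 120, Wald mean coverage and upper-limit miss: 92.6% and 6.4% for 5–10%; 94.1% and 4.4% for 15–20%; 94.4% and 3.7% for 20–30%.

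**Degenerate intervals.** The Wald lower limit is negative when x < z²(1 − x/n). With z² = 3.84 this holds for x = 1 at n ≥ 2, x = 2 at n ≥ 5 and x = 3 at n ≥ 14, and never for x = 4. At x = 0 the width is zero. The chance of 0–3 PEs at 10% and 15% prevalence is 0.16% and under 0.001% for n = 120, 13.7% and 1.5% for n = 60, and 64.7% and 32.2% for n = 30.

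**The case against.** The case against rests on four points.

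- **Chain of assumptions.** The result needs the mMRC groups to receive intervals, the method to be plain Wald, the groups to hold 120 each, and the overall 10–15% to apply within each group. A Wilson interval also rests on a normal approximation, and a continuity correction would restore mean coverage to 95.2%. This stands as a limit on certainty. However, the continuity-corrected upper limit is still too low in 3.9% of samples. If a score interval was meant, the plan need only say so. Equal groups also favour the plan for the smallest group, which cannot exceed 120 of 600.
- **Small effect.** A shortfall of 1.4 points in mean coverage and a shift of about one point in an upper limit decide nothing. This stands, and it limits the weight of the point.
- **Sparse data.** At 120 per group, negative or zero-width intervals are rare. This also stands; they become likely only if groups are as small as about 30. But the plan gives no group sizes and no rule for that case.
- **Wilson's own costs.** Its lower limit is slightly too high, and across five groups it exceeds the nominal rate on that side (14.3% against 11.9%). Using it only for subgroups leaves two methods in one report, although the overall Wald interval has a milder form of the same fault. All true, but Wilson is better balanced between the tails and close to 95% overall.

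**Conclusion.** The concern holds, as a modest point about a secondary endpoint. Read as Wald, the planned interval for PE prevalence by mMRC group averages 93.6% coverage over 10–15% prevalence in equal groups of 120. Its upper limits are too low about twice as often as nominal, and above nominal at every prevalence in that range for every subgroup size computed, 20 to 120. The arithmetic is firm. Its practical importance depends on the Wald reading, on the mMRC groups receiving these intervals, and on group sizes and group prevalences that the documents do not give. No test, stopping decision or sample size rests on these intervals, and the primary estimate is barely affected.

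**What to change.** Add one sentence to the Statistical analysis plan section: *95% CIs for PE prevalence in subgroups, including each mMRC group, will be Wilson score intervals.* Leave the overall-prevalence interval, the P values, the odds ratios and the interim rule as planned.

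If Wilson is also adopted for overall prevalence, state which interval the interim rule uses. That rule begins "If the lower limit of the 95% CI around the prevalence of PE is" and requires at least 20%. The smallest qualifying count among 300 patients is 75 with Wald (0.25 − 1.96 √(0.1875/300) = 20.1%; 74 gives 19.8%) but 74 with Wilson, so the threshold would otherwise move unnoticed.

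The cost is one sentence and standard software. Subgroup intervals will not be symmetric about the estimate, and tables need a footnote because overall and subgroup intervals use different methods. Wilson's lower limit is too high in 3.0% of samples at n = 120 and 3.5% at n = 30, against 2.5% nominal. Clopper-Pearson is the alternative if under-coverage must be excluded, but it is conservative (mean coverage 96.4% at n = 120, 97.5% at n = 30).
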